7.1.3 Packaging, Labeling, and Storage

LX9211 50-mg tablets are packaged in 30 cc high density polyethylene (HDPE) bottles containing pharmaceutical coil and a child resistant polyethylene screw cap with induction seal. Each bottle contains 2 tablets.

LX9211 20-mg tablets are packaged in 30 cc HDPE bottles containing pharmaceutical coil and a child resistant polyethylene screw cap with induction seal. Each bottle contains 20 tablets.

LX9211 tablets in HDPE bottles should be stored at 25°C (77°F); excursions are permitted 15°C to 30°C (59°F to 86°F). Stability testing of all the tablet strengths of LX9211 (50-mg and 20-mg) is ongoing.

7.1.4 Placebo

The placebo dose form is visually similar in color, size, and shape to LX9211 tablets.

Tablet ingredients include silicified microcrystalline cellulose, dibasic calcium phosphate anhydrous, croscarmellose sodium, talc, colloidal silicon dioxide, and hydrogenated vegetable oil.

Placebo tablets are packaged in 30 cc HDPE bottles containing pharmaceutical coil and a child resistant polyethylene screw cap with induction seal. The 50-mg bottle contains 2 placebo tablets while the 20-mg bottle contains 20 placebo tablets.

Placebo tablets in HDPE bottles should be stored at 25°C (77°F); excursions are permitted 15°C to 30°C (59°F to 86°F). Stability testing of placebo tablets is ongoing.

7.2 Prior and Concomitant Medications

7.2.1 Prior Medication

All medications (prescription and OTC) taken within 30 days prior to Screening will be recorded on the eCRF as a prior medication.

7.2.2 Concomitant Medication

All medications and other treatments ongoing or taken from the start of the Screening Period, through the end of the Safety Follow-up Period of the study will be recorded on the eCRF as concomitant medication. This includes any ongoing medications for the treatment patients' PHN (ie, gabapentin, pregabalin, and tricyclic antidepressant medications).

7.3 Prohibited Medication

Use of any new medications prescribed or OTC for treatment of PHN pain is not permitted during the course of the study. Only the acetaminophen provided by the Sponsor as a rescue medicine may be used during the course of the study. The use of personally acquired acetaminophen is prohibited. Use of any opioid medication for the management of PHN within the 2 months prior to Screening is not permitted. **Note:** Brief use (<1 week) of opioid medication for management of non-PHN acute pain (eg, tooth extraction/acute injury) ≥ 2 months prior to Screening Visit is permitted.

All medications, including the study drug, taken by patients during the study will be captured in the source documents and recorded on the eCRF.

7.4 Administration of Study Drug

LX9211 (50-mg and 20-mg) will be supplied in tablet form to be taken orally. A placebo, that is visually similar in appearance to the LX9211 tablets, will be taken by patients assigned to the placebo group.

On Day 1 of the Run-in Period, at the clinic, patients will be given 4 tablets from their bottle of Run-in study drug and will swallow it with 8 ounces (240 mL) of room temperature water. Each patient's hands and mouth will be checked to ensure they have swallowed the tablets. On Days 2 through 14, patients will be instructed to take their daily dose of study drug before the first meal of the day with 8 ounces of room temperature water. If a patient misses a dose by more than 12 hours, that dose should be skipped, and the next dose should be taken as scheduled. No double doses should be taken, and dose reductions are not permitted.

On Day 1 of the double-blinded Treatment Period, at the clinic, patients will be given their loading dose of study drug with 8 ounces (240 mL) of room temperature water to facilitate swallowing. Each patient's mouth will be checked to ensure they have swallowed the tablets. Patients are permitted a light meal prior to arrival at the clinic on Day 1.

On Day 2 to the Week 6 Visit, except for clinic visit days, patients will be instructed to take their daily maintenance dose of study drug before the first meal of the day. Study drug should be taken

with 8 ounces (240 mL) of water and should be taken whole. If a patient misses a dose by more than 12 hours, that dose should be skipped, and the next dose should be taken as scheduled. No double doses should be taken, and dose reductions are not permitted. On the morning of clinic visits, patients are allowed a light meal prior to the visit. For Weeks: 7 through Week 11, the same instructions will be provided to the patient.

The study schema is presented in [Figure 5.1-1](#). Details of study drug administration are provided in [Table 7.4-1](#).

Table 7.4-1 Study Drug Administration

| Treatment Group | Loading Dose (Day 1) * | Daily Maintenance Dose (Day 2 Visit to Week 6/EOT/EW) ** |
|------------------------------------|---|---|
| Group 1: LX9211 200 mg*/20 mg** | 2 x 50-mg LX9211 tablets + 2 x 50-mg LX9211 tablets | 1 x 20-mg LX9211 tablet, qd |
| Group 2: Placebo | 2 x Placebo tablets + 2 x Placebo tablets | 1 x Placebo tablet, qd |

* Loading dose (Day 1)

** Maintenance dose (Day 2 through – Week 6 Visit)

For Weeks 7 through 11 a single tablet will be taken each day.

7.4.1 Treatment Compliance

Patients will be instructed to bring their study drug bottles, including empty bottles and any unused study drug, to each clinic visit. Pill counts will be performed at each clinic visit by a member of the site staff to determine compliance. Pill count will be recorded on the study drug eCRF.

Treatment compliance (%) will be calculated as:

$$\frac{(\text{Number of tablets dispensed} - \text{Number of tablets returned}) \times 100}{\text{Number of tablets expected to be taken}}$$

Number of tablets expected to be taken

The number of tablets expected to be taken is equal to the number of days since the last visit. The Investigator/qualified designee will remind patients at each visit regarding the importance of

taking 1 tablet each morning per protocol. Patients will be deemed “compliant” if their calculated compliance is between 80% and 100%, inclusive. If a patient's compliance is noted to be <80% or >100%, the Investigator will ask the patient for the reason(s) of noncompliance with the dosing instructions, and clearly record the reason(s) in the source documents and on the eCRF and the patient will be reeducated on the need for compliance

If a patient's compliance is noted to be <80% or >100% on 2 consecutive visits, the patient should be counseled by study personnel, and the Sponsor/designee should be contacted to determine study continuation.

7.5 Dose Adjustment

Dose adjustments of any study drug are not permitted or applicable during the study. For safety reasons, should an unacceptable risk related to study drug arise, patients may be discontinued from the study.

8. Study Procedures

A schedule of study assessments with detailed time points is provided in [Appendix A](#).

8.1 Description of Study Assessments

8.1.1 Patient-reported Outcomes

Three patient-reported outcomes (PROs), ZBPI, PGIC and NPSI, measures will be assessed on a validated electronic device completed at the time of the clinic visit as specified in [Appendix A](#). The ZBPI, a 9-item questionnaire assesses the severity of pain and its impact on functioning in patients with PHN. The PGIC, a 7-point rating scale will assess patient's belief about the overall improvement experienced by the patient at the end of treatment. The NPSI, a 12-item questionnaire, assesses the different components of neuropathic pain syndromes (ie, spontaneous ongoing and paroxysmal pain, evoked pain, paresthesia/dysesthesia). Ten items related to different pain descriptors (eg, burning, squeezing, electric-shock, stabbing, tingling) allows assessment of the different dimensions of neuropathic pain and 2 items on frequency and duration of pain.

8.1.2 Qualitative Patient Interview

A telephone qualitative interview substudy will be conducted for approximately 30 patients within 2 weeks following the Week 6 Visit or early withdrawal visit for patients within the US.

The purpose of the phone interview will be to gain insight and understanding of patients' experiences with symptoms of PHN and to assess relevance and clinical meaningfulness of symptom improvements. (eg, reduction in pain).

The qualitative patient interview will be performed as specified in [Appendix A](#).

8.1.3 Clinical Laboratory Assessments

Clinical laboratory assessments will include, at a minimum, blood chemistry (albumin, alkaline phosphatase, alanine transaminase [ALT], amylase, aspartate transaminase [AST], total bilirubin, glucose, blood urea nitrogen [BUN], calcium, carbon dioxide, chloride, creatinine, magnesium, phosphorus, potassium, sodium, total protein, and uric acid), lipid panel (high-density lipoprotein (HDL), low-density lipoprotein (LDL), total cholesterol, triglycerides, creatinine phosphokinase [CPK]), hematology (complete blood count [CBC] with differential, and platelet counts), and urinalysis (including appearance, color, glucose, ketones, nitrite, pH, protein, specific gravity, occult blood, leukocyte esterase, bilirubin, and urobilinogen). Urine microscopy will only be performed if any of the following are present in the urine sample: occult blood, leukocyte esterase, protein, or nitrite. The microscopy will include analysis for the presence of WBC, red blood cells, epithelial cells, bacteria, casts, and crystals.

Additional assessments such as: pregnancy tests [females only]), and a urine screen (drugs of abuse and THC) will be done at time points specified in [Appendix A](#).

The incidence of clinically significant laboratory values, as well as clinically significant shifts in laboratory values, should be reported as an AE ([Section 9.1.1](#)) and followed as described in [Section 9.5](#); retests should be performed as frequently as clinically indicated.

8.1.4 Pharmacokinetic Assessments

Plasma samples from all patients will be analyzed for LX9211 C_{p2hr} and C_{trough} levels. Blood draws will be performed at time points indicated in the schedule of events ([Appendix A](#)).

[REDACTED]

8.1.5 Safety Assessments

In addition to the clinical laboratory assessments described in [Section 8.1.1](#), monitoring of AEs is also considered a safety assessment and is described in detail in [Section 9](#). Clinically significant changes compared with Baseline findings for these variables may be reported as AEs on the eCRF. Clinically significant changes compared with Baseline values, which are determined to be AEs should be followed until the event has resolved, the condition has stabilized, etiology of the event is determined to be not related to study drug, or the patient is lost to follow-up. In case a patient reports an AE, study drug may be held for up to 3 days to assess resolution, rather than discontinuing patient permanently from study participation. If the AE improves or resolves, study drug may be resumed. Prior to discontinuing a patient permanently from study participation, the Investigator should discuss the case with the Medical Monitor.

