3.4 Clinical Trials of LX9211 in Humans

Three clinical studies have recently completed: LX9211.1-101-NRM, A Phase 1, Randomized, Double-blind, Placebo-controlled Ascending, Single-dose Study to Determine the Safety and Tolerability of Orally Administered LX9211 in Healthy Human Participants (SAD); LX9211.1-102-NRM, A Phase 1, Randomized, Double-blind, Placebo-controlled Ascending Multiple-dose Study to Determine the Safety and Tolerability and Pharmacokinetics of Orally Administered LX9211 in Healthy Volunteers (MAD); and LX9211.1-103-NRM, A Phase 1, Open-label, Nonrandomized, 2-part Study to Evaluate the Absorption, Metabolism, Excretion, Mass Balance, and Absolute Bioavailability of ^{14}C -LX9211, Following Oral and Intravenous Administration in Healthy Male Subjects.

The SAD and MAD studies included females of nonchildbearing potential and males between the ages of 18 to 65 years. A total of 146 subjects were enrolled in the 2 studies, 112 of whom were randomly assigned to receive LX9211.

The results from the SAD study showed that LX9211 was generally well tolerated in healthy normal subjects at single doses up to 300 mg. Results from cohorts exposed to single-dose LX9211 up to 300 mg are summarized as follows:

Adverse events were mild to moderate in intensity; there were no severe AEs, deaths, SAEs, or withdrawals due to AEs. The most common AEs were dizziness and headache. One subject in the 300 mg single-dose cohort experienced orthostatic tachycardia with an onset at 1-hour postdose and which lasted for 8 days. This event was reported by the Investigator as mild in intensity and related to study drug.

Systemic exposure to LX9211 (C_{\max} , AUC_{0-24} , AUC_{0-96} , and $AUC_{0-\infty}$) increased from 5 to 300 mg in an apparent dose-proportional manner when examined as the log functions of dose and exposure. Median T_{\max} of LX9211 was approximately 8-12 hours postdose and the mean $t_{1/2}$ ranged from 143 to 197 hours (6 to 8 days).

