Based on the pharmacokinetic (PK) profile of LX9211 in the SAD study, subjects in the MAD study were given a loading dose on Day 1, followed by a daily maintenance dose on Days 2-14. This dosage regimen permitted steady state to be achieved quickly and then maintained for the duration of the study. Results from this study showed that LX9211 was well tolerated in healthy normal subjects receiving multiple doses (14 days) up to 200 mg loading dose. All AEs were mild in intensity; there were no severe AEs, deaths, or SAEs. One patient discontinued due to reported AEs: allergic rash, urticaria, and angioedema. All AEs were assessed as mild and

resolved within a few days after being treated with a single oral dose of diphenhydramine. Overall, the AEs observed in the MAD study were similar to those reported in the SAD study. In both studies, the most common AEs were headache and dizziness in patients treated with LX9211, with the events occurring at higher frequency at doses at or above 100 mg. With few exceptions, these events occurred 1-3 days after dosing, lasted for 1-2 days, were considered mild in intensity, and resolved spontaneously. No clinically significant comprehensive metabolic panel (CMP), UA findings, or bladder dysfunction-related AEs were reported in any subject treated with LX9211 in the SAD or MAD studies with LX9211.

In study LX9211-103, a cohort of 6 male subjects was exposed to a single oral dose of ^{14}C -LX9211 (nominal 50 mg free drug, approximately 52uCi). Drug-related material in urine and feces was collected for up to 34 days. The mean total recovery of administered radioactivity was 77.9%, with 48.7% recovered in urine and 29.2% recovered in feces. There were no serious adverse events (SAEs) and the adverse events (AEs) experienced, were similar to those seen in the SAD and MAD studies; all were mild in severity. In the same study, a separate cohort of 6 subjects underwent an evaluation to establish the absolute oral bioavailability of LX9211. A single oral dose of 50 mg of LX9211 was administered, followed by an intravenous microdose infusion of ^{14}C -9211 (50 μg /200nCi). The mean oral bioavailability of LX9211 was 89.4%. Again, there were no SAEs and the AEs experienced were similar to those seen in the SAD and MAD studies; all were mild in severity.

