3.5 Rationale for Current Study

3.5.1 Rationale for Selection of Dose

The loading and maintenance dose level of LX9211 selected for evaluation in the current study was chosen based upon the safety, tolerability, and PK data observed from the prior single-dose and multiple-dose Phase 1 studies.

The doses studied in the SAD and MAD studies, in healthy volunteers, ranged from 5 to 300 mg. Single-dose administration demonstrated linear PK up to the highest tested dose (300 mg). There were no deaths, SAEs, discontinuations due to an AE, AEs of severe intensity, or any clinically significant laboratory, vital sign, physical exam (PE), or electrocardiogram (ECG) findings.

Multiple-dose administration demonstrated linear PK up to the highest tested dose (200 mg). There were no deaths, SAEs, discontinuations due to an AE, AEs of severe intensity, or any clinically significant laboratory, vital sign, PE, or ECG findings.

Based on the observed safety and tolerability data from single doses up to 300 mg and multiple doses up to 200 mg for 14 days, the dose level selected in this study, 200 mg loading dose

followed by 20 mg maintenance doses, respectively, are expected to be well tolerated and represent an adequate range for dose exploration.

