9.2.2 Causality

Causality assessment is a determination of whether there is a reasonable possibility that the study medication caused an AE. Factors that should be considered in causality assessment include, but are not limited to, temporal relationship, dechallenge/rechallenge information, association (or lack of association) with underlying disease or concomitant medication, biological plausibility, and previous observation or lack of with the study medication or other medication(s) in the same class as the study medication.

For each AE, the Investigator will assess the causal relationship between the study medication and the AE using their clinical expertise and judgment according to the most appropriate description as follows:

- **Not related**: The AE does not follow a reasonable temporal relationship to administration of the study medication, or an alternative etiology (eg, underlying disease, complications, concomitant drugs, or concurrent treatment) is much more likely
- **Unlikely related**: The AE has an improbable temporal relationship to administration of the study medication, or an alternative etiology (eg, underlying disease, complications, concomitant drugs, or concurrent treatment) is more likely

- **Possibly related**: The AE follows a reasonable temporal relationship to administration of the study medication (including the course after withdrawal of the drug), and an alternative etiology (eg, underlying disease, complications, concomitant drugs, or concurrent treatment) is equally or less likely
- **Probably related**: The AE follows a reasonable temporal relationship to administration of the study drug (including the course after withdrawal of the drug), and an alternative explanation (eg, underlying disease, complications, concomitant drugs, or concurrent treatment) is unlikely
- **Definitely related**: The AE follows a plausible temporal relationship to administration of the study medication (including the course after withdrawal of the drug) and alternative etiology (eg, underlying disease, complications, concomitant drugs, or concurrent treatment) can be ruled out. Positive rechallenge (ie, reappearance or worsening of the AE after the study drug is reintroduced) or a response pattern known to be associated with administration of the study drug provides further evidence of a definitive causality assessment.

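### Protocol 8.1.5 allows study drug to be resumed after any adverse event that improves during a short hold, with no limit on rechallenge after angioedema or other systemic hypersensitivity

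*Protocol*

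**What the plan says.** Protocol 8.1.5 sets one route for a patient who reports an adverse event: "study drug may be held for up to 3 days to assess resolution, rather than discontinuing patient permanently from study participation". It continues: "If the AE improves or resolves, study drug may be resumed". The section names no event, severity grade or causality rating that is exempt. Its one consultation step concerns stopping: "Prior to discontinuing a patient permanently from study participation, the Investigator should discuss the case with the Medical Monitor". No equivalent step is asked for before a restart.

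Protocol 3.4 describes the multiple-dose Phase 1 study in healthy volunteers: "One patient discontinued due to reported AEs: allergic rash, urticaria, and angioedema". The events were rated mild and "resolved within a few days after being treated with a single oral dose of diphenhydramine". The text does not say whether this participant received LX9211 or placebo, at what dose, or how causality was rated.

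Protocol 3.5.1 summarises the same multiple-dose experience differently: "Multiple-dose administration demonstrated linear PK up to the highest tested dose (200 mg). There were no deaths, SAEs, discontinuations due to an AE".

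**The concern.** The Phase 1 reaction was mild and improved within days. That is the kind of course 8.1.5 allows back onto drug. A patient in this trial with the same reaction could be held for up to 3 days, improve, perhaps with an antihistamine, and resume daily dosing at home. No second opinion would be required.

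Angioedema can recur, and a mild first episode does not guarantee a mild second one. About 30 sites, all blinded, would each make the restart decision under a rule that treats angioedema like a headache. What is at stake is the safety of individual patients. The primary efficacy analysis is barely affected either way.

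**Working it through.** The plan states no figure for this point. The check is mainly a reading of the sections, with a small decay calculation for context.

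**1. Does any other section supply the missing limit?**

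| Section | Content | Bars restart after angioedema? |
|---|---|---|
| Protocol 6.2, exclusion 17 | Earlier reactions to inactive ingredients, at entry only | No |
| Protocol 6.3 | Withdrawal if the Investigator judges continuation medically unacceptable | No, discretionary |
| Protocol 6.5 | No clinical stopping rules; points to 6.3 and 6.4 | No |
| Protocol 7.5 | Patients may be stopped for unacceptable drug-related risk | No, discretionary |
| Protocol 9.1.1 | Counts hypersensitivity reactions as adverse events | No, definition only |
| Protocol 9.1.2 and 9.4 | Important medical events may be serious; serious events go to the Sponsor within 24 hours | No, reporting only |
| Protocol 9.3.1 | Pregnancy must end participation | Concerns pregnancy only |
| Protocol 9.3.2 | No adverse events of special interest | No |
| Protocol 9.4 | Medical Monitor is the contact for patient-management questions | No; available, but not required before restart |
| Protocol 6.4.1 and SAP 7.8 | DMC safety reviews and monthly unblinded summaries of serious events | No, not individual restart decisions |
| SAP 7.7.2 | Descriptive count of drug interruptions due to adverse events | No |

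No section closes the gap. A mild event not classed as serious would fall outside both the 24-hour report and the monthly summaries.

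**2. How much drug is present when the restart decision is made?**

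Input: the half-life in Protocol 3.4, which "ranged from 143 to 197 hours (6 to 8 days") in the single-dose study. Assumption: simple first-order decline at that half-life, so the fraction remaining is 0.5^(t / half-life).

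- At 72 h after the last dose: 0.5^(72/143) = 0.705 and 0.5^(72/197) = 0.776, so about 71% to 78% remains.
- At 96 h, when dosing restarts after three missed daily doses: 0.5^(96/143) = 0.628 and 0.5^(96/197) = 0.713, so about 63% to 71% remains.
- Time to fall to 25% (two half-lives): 2 × 143/24 = 11.9 days and 2 × 197/24 = 16.4 days.

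A 3-day hold therefore removes only about a quarter of the drug (22% to 29%). A restart continues exposure that has hardly fallen.

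**3. What would a stricter rule cost in patients?**

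With 37 patients per arm (Protocol 10.1), each extra treatment stop is 1/37 = 2.7% of an arm. The planned 15% dropout corresponds to 0.15 × 37 = 5.55, or about 5.6 patients per arm.

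**The case against.** The strongest reply is that 8.1.5 is permissive. It says drug may be held and may be resumed, and Protocol 6.3 and 7.5 leave the Investigator free to stop. Angioedema is visible, and a physician would be expected to act on it. A severe reaction would also be escalated as a serious event. All of this stands. A reader might infer that the protocol directs rechallenge after angioedema; it does not. What remains is that nothing forbids it and nothing requires a second opinion first, and mild events are where the gap lies.

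The Phase 1 evidence is thin: one participant, events rated mild, arm and causality unstated. Of the 146 single- and multiple-dose participants, 112 were assigned LX9211, so 146 − 112 = 34 were not. A reader might infer that LX9211 causes angioedema, or attach a rate to it. The documents support neither, and the Investigator Brochure, to which the protocol refers for detail, was not available.

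The half-life argument also has limits. Protocol 9.2.2 lists "temporal relationship, dechallenge/rechallenge information" among several causality factors, but 8.1.5 gives the purpose of the hold as assessing resolution. A reader might infer that sites are told to treat improvement as evidence against the drug; no section says so. Slow clearance also applies whether or not dosing is stopped. Stopping avoids later doses but does not remove the drug already present. The figures show that the hold is a weak test, and no more.

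Bladder events have their own monitoring text in Protocol 9.1.1.1 although no clinical case was reported in the single- and multiple-dose studies. That comparison adds little: the text follows from dog tissue findings that could be silent, whereas rash and swelling are seen and reported.

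**Conclusion.** The point holds as a missing limit on rechallenge. Protocol 8.1.5 covers every adverse event, no other section of the protocol or SAP excepts angioedema or other systemic hypersensitivity, and no Medical Monitor contact is required before resuming. The one relevant event in the programme's own background section had a course that this rule would let back onto drug.

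The change is worth making, but this is not a fatal flaw. Investigator discretion is intact, the triggering event is single and mild, and no incidence can be estimated. The decay figures rest on first-order elimination at the single-dose half-life in healthy volunteers.

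The conflict between 3.4 and 3.5.1 is a separate correction to background text. A reader might take it as raising the seriousness of the restart rule, but the gap in 8.1.5 would be the same if the two sections agreed.

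**What to change.** In Protocol 8.1.5 and 6.3:

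- Require permanent discontinuation of study drug, without rechallenge, for angioedema, anaphylaxis or generalised urticaria, unless the Investigator and Medical Monitor agree on a clear alternative cause. Making the stop the default avoids resting the decision on one blinded causality rating.
- Require Medical Monitor agreement before resuming drug after any other suspected allergic event.
- State that these patients stop study drug only and continue the daily diary to Week 6. SAP 6.1.1 needs at least 4 diary scores in Days 36 to 42 for a Week 6 pain score, so a return for the clinic visit alone would not supply it.

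Separately, as an editorial correction, reconcile 3.5.1 with 3.4 and give the arm and dose of the participant who stopped.

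The cost is a short amendment, a site memo and possibly a few extra treatment discontinuations. Dose, sample size and the efficacy analysis are unchanged.
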